10.2 Results Reporting on ClinicalTrials.gov

At study activation, this study will be registered within the "ClinicalTrials.gov" website. The Primary and Secondary Endpoints (i.e., "Outcome Measures") along with other required information for this study will be reported on ClinicalTrials.gov. For purposes of timing of the Results Reporting, the initial estimated completion date for the Primary

Endpoint of this study is 24 months after the study opens to accrual, including 15 months to accrual, about 9 months for the last patient enrolled to finish protocol treatment, and about 6 months for data cleaning and analysis. The definition of “Primary Endpoint Completion Date” (PECD) for this study is at the time that all registered patient have been off treatment.

10.3 Adverse Event Data

This study is GCC investigator initiated and is not sponsor supported. All adverse events will be reported via ONCORE. Serious unexpected adverse events will be reported to the UMB IRB via CICERO according to IRB guidelines.

- Monitoring and scoring of adverse events will be performed as per the National Cancer Institute (NCI) Common Terminology Criteria for Adverse Events (CTCAE) version 4.0. A copy of the CTCAE version 4.0 can be downloaded from the CTEP website:
http://ctep.cancer.gov/protocolDevelopment/electronic_applications/ctc.htm.
- All Adverse Events will be reported in ONCORE per DSMQAC.
<\\stccl1srv7\radonc\protocol\Protocol\DSMQAC>
<https://oncoreweb1.umm.edu/login/>
- The UMB IRB will be notified per UMB Human Research Protections Office (HRPO) guidelines.

http://hrpo.umaryland.edu/includes/Study_Tool_Docs/Reportable-New-Information_6-28-11.pdf

Serious Adverse Events that meet the University of Maryland Baltimore Institutional Review Board (UMB IRB) **REPORTABLE NEW INFORMATION** (RNI) will reported via <https://cicero.umaryland.edu/>

REPORTABLE NEW INFORMATION (University of Maryland, Baltimore
Revision Date: 6/28/11)

Report the information items that fall into one or more of the following categories to the IRB within 5 business days using this form:

Information that does not fall under any of the categories does not require reporting to the IRB.

1) Information that indicates a new or increased risk, or a safety issue. For example:

a) New information (e.g., an interim analysis, safety monitoring report, publication in the literature, sponsor report, or investigator finding) indicates an increase in the frequency or magnitude of a previously known risk, or uncovers a new risk.

b) An investigator brochure, package insert, or device labeling is revised to indicate an increase in the frequency or magnitude of a previously known risk, or describe a new risk

- c) Withdrawal, restriction, or modification of a marketed approval of a drug, device, or biologic used in a research protocol
- d) Protocol violation that harmed subjects or others or that indicates subjects or others might be at increased risk of harm
- e) Complaint of a subject that indicates subjects or others might be at increased risk of harm or at risk of a new harm
- f) Any changes significantly affecting the conduct of the research
- 2) Any harm experienced by a subject or other individual, which in the opinion of the investigator are **unexpected** and **probably related** to the research procedures.
 - a) A harm is “**unexpected**” when its specificity or severity are inconsistent with risk information previously reviewed and approved by the IRB in terms of nature, severity, frequency, and characteristics of the study population.
 - b) A harm is “**probably related**” to the research procedures” if in the opinion of the investigator, the research procedures more likely than not caused the harm.
- 3) Non-compliance with the federal regulations governing human research or with the requirements or determinations of the IRB, or an allegation of such non-compliance.
- 4) Failure to follow the protocol due to the action or inaction of the investigator or research staff.
- 5) Breach of confidentiality.
- 6) Change to the protocol taken without prior IRB review to eliminate an apparent immediate hazard to a subject.
- 7) Incarceration of a subject in a study not approved by the IRB to involve prisoners.
- 8) Complaint of a subject that cannot be resolved by the research team.
- 9) Premature suspension or termination of the research by the sponsor or the investigator.
- 10) Unanticipated adverse device effect (any serious adverse effect on health or safety or any life-threatening problem or death caused by, or associated with, a device, if that effect, problem, or death was not previously identified in nature, severity, or degree of incidence in the investigational plan or application (including a supplementary plan or application), or any other unanticipated serious problem associated with a device that relates to the rights, safety, or welfare of subjects.)
- 11) Audit, inspection, or inquiry by a federal agency.
- 12) Written reports of study monitors.
- 13) For Veterans Administration (VA) research all local or internal unanticipated serious adverse events. (Note: VA is not a site for recruitment for this clinical trial.)

10.5 Additional Instructions or Exclusions to Adverse Event Expedited Reporting Requirements for Commercial Agents in a non-IND trial

- Treatment expected adverse events include those listed in the Informed Consent

Form (ICF) and in the package inserts for fluorouracil, leucovorin, and oxaliplatin.

- Grade 3 or 4 myelosuppression and hospitalization resulting from such do not require expedited reporting via CICERO but will be reported in ONCORE and will be submitted as part of study results.
- Other grade 1-4 events that are expected do not require expedited reporting via CICERO, even if they result in hospitalization.
- Grade 4 events that are unexpected and that are at probably related (per UMB IRB definition) to treatment must be reported via CICERO within 5 calendar days per UMB IRB guidelines.
- All new malignancies should be reported to the IRB whether or not they are thought to be related to either previous or current treatment. All new malignancies should be reported, i.e., solid tumors (including non-melanoma skin malignancies), hematologic malignancies, myelodysplastic syndrome (MDS)/acute myelogenous leukemia (AML), and *insitu* tumors. In CTCAE version 4.0, the new malignancies (both second and secondary) may be reported as one of the following:
 - (1) Leukemia secondary to oncology chemotherapy,
 - (2) Myelodysplastic syndrome,
 - (3) Treatment-related secondary malignancy, or
 - (4) Neoplasm other, malignant (grade 3 or 4).Whenever possible, the IRB reports for new malignancies should include, tumor pathology, history of prior tumors, prior treatment/current treatment including duration, any associated risk factors or evidence regarding how long the new malignancy may have been present, when and how the new malignancy was detected, molecular characterization or cytogenetics of the original tumor (if available) and of any new tumor, and new malignancy treatment and outcome, if available.
- All pregnancies and suspected pregnancies occurring in female patients or in the partner of a male patient during therapy or within 28 days after completion of treatment on GCC 1314 must be reported to the IRB. In CTCAE version 4.0, use the event term, "*pregnancy, puerperium, and perinatal condition-other, fetal exposure (grade4)*".
- IRB reports should be amended upon completion of the pregnancy to report pregnancy outcome (e.g. normal, spontaneous abortion, therapeutic abortion, fetal death, congenital abnormalities).
- The IRB report should be amended for any neonatal deaths or complications occurring within 28 days of birth independent of attribution. Infant deaths occurring after 28 days considered to be related to in utero exposure to the agents used in this trial should be reported to the IRB.

10.6 Assessment of Attribution

The following attribution categories are utilized when assessing whether an adverse event is related to a medical treatment or procedure:

- Definite – The adverse event is clearly related to the agent(s).
- Probable – The adverse event is likely related to the agent(s).
- Possible – The adverse event may be related to the agent(s).
- Unlikely – The adverse event is doubtfully related to the agent(s).
- Unrelated – The adverse event is clearly NOT related to the agent(s).

11.0 DOSE MODIFICATION BASED ON ADVERSE EVENTS

11.1 Radiation therapy

Treatment interruptions are discouraged although may be necessary due to acute severe complications. Documentation must be made for any such complications including the reason and length of the treatment interruption.

If chemotherapy is held, then radiation therapy will be held. If radiation is held, then chemotherapy would continue per physician discretion.

Radiation therapy may be held for grade 4 cellulitis of the perineum or grade 4 neutropenia or other radiation-associated toxicity. Radiation should be restarted subsequent to recovery at the discretion of the treating radiation oncologist as per standard practice.

Table 11.1 Radiation therapy modifications based on adverse events

System/Organ/Class	Adverse Event	Dosage Change
Blood/lymphatic system disorders	Thrombocytopenia	Grade 2 – Continue at current dose Grade 3 – Hold until recovery ≤ grade 2 then resume Grade 4 – Hold until recovery ≤ grade 2 (platelets ≥ 75 x 10 ⁹ /L) then resume
	Neutropenia	Grade 3 or 4 – Hold until recovery ≤ grade 2 then resume
	Febrile Neutropenia	Grade 3 or 4 – Hold until resolution of fever and neutropenia ≤ grade 2. Hold until the ANC ≥ 1500/mm ³ and fever has resolved then resume
Gastrointestinal disorders	Diarrhea	Grade 1 or 2 – Continue at current dose Grade 3 – If grade 3 for >4 days, hold until recovery ≤ grade 2 then resume Grade 4 – Hold until recovery ≤ grade 2 then resume

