5.2 Radiation therapy

5.2.1 Simulation: Will be performed prior to initiation of therapy with patients in the supine position and arms above the head. One Vac-Lock bag will be used for positioning and immobilization placed at the level of the pelvis. No oral or IV contrast is required. CT simulation from the cranial extent of L1 to the level of the lesser trochanter will be performed to ensure adequate coverage and dosimetric parameters.

5.2.2 Volumes: The gross tumor volume (GTV) should be contoured using all available imaging as well as information from physical examination and proctoscopy.

The clinical target volume (CTV) should include the GTV as well as elective lymph node regions (internal iliac, mesorectal, presacral). Since patients with low lying rectal tumors and T4 rectal tumors will not be included in this study, the external iliac and inguinal lymph nodes should not be included as they are not felt to be at a significant clinical risk of subclinical involvement. A planning target volume (PTV) should be created using a 0.5 cm uniform expansion from the CTV to account for daily set up variability provided daily kilovoltage (kV) imaging is used for image guidance. If daily kV imaging is not available, then larger PTV margins should be used based on the discretion of the treating physician. Normal structures to be contoured include small bowel (up to 1 cm superior to PTV), bladder, femoral heads, and pelvic bones (including the sacrum, ilium, ischium, and pubic bones as a surrogate for bone marrow).

5.2.3 Technique: To limit dose to bone marrow, LDFRT will be delivered using intensity modulated radiation therapy (IMRT). IMRT may be delivered using either static beams or volumetric-modulated arc therapy (VMAT). Since the total prescribed radiation dose used in this study is well below the established tolerance levels of all normal tissues that will be contoured, no specific normal dose constraints should be used. However, a priority should be made to limit the volume of the pelvic bones (as a surrogate for bone marrow) receiving the prescription dose.

5.2.4 Dose: 40 cGy fractions will be administered twice daily on Days 1 and 2 of each cycle of FOLFOX with each radiation fraction being delivered [a minimum of 4](#) hours apart. This will be repeated every 2 weeks for a total dose of 960 cGy.

5.2.5 Treatment Planning Objectives:

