11.2 Chemotherapy

The patient will discontinue FOLFOX and be referred for treatment off protocol if the patient requires dose reduction beyond level -2 during cycles 1-5 of preoperative therapy or if FOLFOX is held due to toxicity for more than 30 days from the previous cycle.

The precise dose modification schema used and the symmetry of dose modification may be left to the discretion of the treatment physician.

Table 11.2 FOLFOX dose levels

Dose level*	5-FU infusion	5-FU bolus	Oxaliplatin
0	1200 mg/m ² /day x 2 days (2400 mg/m ² over 48 hours)	400 mg/m ²	85 mg/m ²
-1	960 mg/m ² /day x 2 days (1920 mg/m ² over 48 hours)	320 mg/m ²	65 mg/m ²
-2	800 mg/m ² /day x 2 days (1600 mg/m ² over 48 hours)	270 mg/m ²	50 mg/m ²
-3	680 mg/m ² /day x 2 days (1360 mg/m ² over 48 hours)	230 mg/m ²	40 mg/m ²

*Dose level 0 refers to the starting dose

Table 11.3 FOLFOX dose modifications based on adverse events

System/organ/class	Adverse event	Agent	Dosage change
Blood and lymphatic systemic disorders	Neutropenia grade ≥2 and/or Thrombocytopenia grade ≥ 2	5-FU Oxaliplatin	Hold up to 16 days until ANC ≥ 1200 K/mcL. If recovered in ≤ 16 days, then resume at next lower dose level. Hold up to 16 days until platelets ≥ 75,000 K/mcL. If recovered in ≤ 16 days, then resume at next lower dose level.
Gastrointestinal disorders	Nausea grade 2 Nausea grade 3	Oxaliplatin	Intensify antiemetic therapy and proceed with FOLFOX at current dose level. Maximal antiemetic therapy includes a 5-HT inhibitor in addition to Compazine, lorazepam, aprepitant, and dexamethasone If resolved to < grade 2 on day of treatment, may proceed with intensification of antiemetic therapy and current dose level of FOLFOX. If not resolved to < grade 2 on day of therapy, intensify antiemetic regimen

	Nausea grade 4	5-FU Oxaliplatin	and proceed with FOLFOX when resolved to < grade 2. May decrease oxaliplatin one dose level if not responsive to maximal antiemetic support.
Vomiting grade 2	If resolved to < grade 2 on day of treatment, may proceed with intensification of antiemetic therapy and current dose level of FOLFOX. If not resolved to < grade 2 on day of therapy, intensify antiemetic regimen and proceed with FOLFOX when resolved to < grade 2. Decrease oxaliplatin one dose level if not responsive to maximal antiemetic support.		

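### Section 11.1 and Table 11.1 give different radiation hold rules for neutropenia, and the link to the FOLFOX hold adds a third threshold; the conflict matters mainly when FOLFOX is not held and at restart

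*Combined protocol and SAP*

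**What the plan says.** Four parts of the protocol bear on whether radiation is given to a patient with neutropenia.

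- **Section 11.1, paragraph.** "Radiation therapy may be held for grade 4 cellulitis of the perineum or grade 4 neutropenia or other radiation-associated toxicity". On restarting: "Radiation should be restarted subsequent to recovery at the discretion of the treating radiation oncologist as per standard practice".
- **Table 11.1, neutropenia row.** "Grade 3 or 4 – Hold until recovery ≤ grade 2 then resume".
- **Section 11.1, link to chemotherapy.** "If chemotherapy is held, then radiation therapy will be held". The reverse does not apply: if only radiation is held, continuing chemotherapy is a matter for the physician.
- **Table 11.3, FOLFOX.** The trigger is "Neutropenia grade ≥2 and/or Thrombocytopenia grade ≥ 2" and the action for neutrophils is "Hold up to 16 days until ANC ≥ 1200 K/mcL", followed by resumption at the next lower dose level if recovery comes in time.

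Two further provisions determine how these interact. Section 11.2 loosens the FOLFOX table: "The precise dose modification schema used and the symmetry of dose modification may be left to the discretion of the treatment physician". Section 5.1.2 likewise leaves chemotherapy modification to the medical oncologist and puts no restriction on modifying cycle 6. Section 5.2.4 ties radiation to the chemotherapy cycle: "40 cGy fractions will be administered twice daily on Days 1 and 2 of each cycle of FOLFOX".

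**The concern.** The paragraph and the table in section 11.1 address the same event and differ in three respects: the grade at which a hold applies, whether the hold is optional or directed, and what permits a restart. Nothing in the section says which takes precedence. The paragraph's open category of other radiation toxicity does not settle the matter, because it is governed by the same permissive verb.

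Neutropenia is a foreseen event here. Section 1.2.3 justifies marrow-sparing planning on the ground that FOLFOX is more toxic to the marrow than 5-FU alone. Two centre physicians could both follow section 11.1 and act differently on the same count. Irradiating at grade 3 or 4 is compatible with the paragraph but departs from Table 11.1, so it is also unclear whether it would count as a failure to follow the protocol, which is on the list of reportable items in section 10.3.

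**Working it through.** No formula applies and the plan states no figure to reproduce. The check sets the rules side by side and follows a patient through them.

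**The three routes to a radiation hold**

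| Source | Neutropenia grade | Force | Restart |
|---|---|---|---|
| 11.1 paragraph | 4 named; others only through the open category | optional | after recovery, at the radiation oncologist's discretion |
| Table 11.1 | 3 or 4 | directed | recovery to grade 2 or lower |
| 11.1 link plus Table 11.3 | 2 or higher | radiation follows any FOLFOX hold | FOLFOX: neutrophil count threshold, within 16 days |

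The last two restart criteria are on different scales, one a toxicity grade and the other a count. The protocol refers to CTCAE version 4.0 without reproducing its grade limits, so the documents alone do not show whether the two coincide.

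**Following the cases**

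1. *Grade 3 or 4 on the Day 1 count, FOLFOX held under Table 11.3.* The paragraph allows a hold, Table 11.1 directs one, and the link requires one. Radiation is held on every reading. Appendix I schedules the blood count in the Day 1 column of each cycle, and radiation falls only on Days 1 and 2, so one count informs both treatments. This is the ordinary case.
2. *Grade 3, FOLFOX given under the discretion in 5.1.2 or 11.2.* The link is silent because chemotherapy was not held. The paragraph does not name grade 3, so a hold is neither required nor forbidden. Table 11.1 directs a hold. The two lines conflict in force and in threshold.
3. *Grade 4, FOLFOX given under the same discretion.* Both lines name the event. One makes the hold optional and the other directs it.
4. *Grade 3 or 4 found after that cycle's chemotherapy has started, with fractions still to give.* If the chemotherapy is not then held, the link is again silent and the conflict is as in cases 2 and 3. Appendix I schedules no Day 2 count, so this needs an unscheduled one.
5. *Grade 2, FOLFOX held under Table 11.3.* The link holds radiation. Table 11.1 sets no hold at grade 2 and treats grade 2 as sufficient recovery to resume.
6. *Restart after any hold.* The paragraph relies on discretion, Table 11.1 on a grade, and Table 11.3 on a count for the FOLFOX cycle to which radiation is tied. The link says when radiation stops but not when it starts again.

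**Dose concerned.** Each cycle carries 2 fractions × 2 days × 40 cGy = 160 cGy, and 6 × 160 = 960 cGy, which matches section 5.2.4. One cycle is therefore 160/960, or one sixth of the planned dose. This is the dose scheduled in an affected cycle, not a measured loss.

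**The case against.** The strongest reply is that the link sentence and Table 11.3 already protect the patient. FOLFOX is held from grade 2, radiation follows, and the disagreement inside section 11.1 never comes into play. The paragraph does not order treatment at grade 3, so a physician who holds under Table 11.1 breaches nothing in it. The restart wording can also be read together, with the table defining recovery and the oncologist deciding after it.

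Much of this stands. A reader might infer from section 11.1 alone that a patient with grade 3 neutropenia is irradiated or not according to which line is consulted, and that every such event on a radiation day is affected. The documents do not support that: no line directs treatment at grade 3, and in the ordinary case the link produces a hold on any reading. A reader might also infer that each event costs 160 cGy. That is not shown either. Table 11.1 provides for resumption, and the definitions after Table 11.3 describe a hold as treatment that can be made up within the cycle, although applying that definition to Table 11.1 is an inference.

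The reply does not dispose of the point. The FOLFOX hold is not clearly binding, given 5.1.2 and 11.2. Section 11.1 foresees radiation being held while chemotherapy continues, so its own rules have to work unaided. Relying on the link also brings in a threshold that Table 11.1 does not share. The joint reading of the restart wording is plausible, but the protocol does not state it.

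**Conclusion.** The inconsistency is real, but its reach is limited. Three thresholds apply to radiation (grade 4, grade 3 or 4, and grade 2 or higher through the link), with two levels of force and no single restart criterion. It affects what happens to a patient when FOLFOX is not held, when neutropenia is found after the cycle's chemotherapy has started, and when radiation is to be restarted. When FOLFOX is held under Table 11.3, the disagreement within section 11.1 makes no difference to whether radiation stops.

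The number of patients involved cannot be estimated, because the documents give neither the frequency of grade 3 or 4 neutropenia nor how often FOLFOX would be given despite it. Lost radiation dose is not demonstrated. The pCR definition, the sample size of 30, the confidence interval width of 0.36 and the two-stage rule are untouched. The conclusion assumes that the discretion wording in 5.1.2 and 11.2 allows FOLFOX to proceed where Table 11.3 would hold it. If the sponsor regards Table 11.3 as binding, the second and third cases fall away, and the mid-cycle, grade 2 and restart discrepancies remain. The correction should be made because this is a safety rule that contradicts itself.

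**What to change.** Reconcile three things together: the section 11.1 paragraph, the neutropenia row of Table 11.1, and the chemotherapy–radiation link as it operates through Table 11.3. The revised text should state:

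- one neutropenia threshold for holding radiation, and whether the hold is mandatory or optional;
- one restart criterion for radiation, and how it relates to the neutrophil count that releases FOLFOX;
- what applies to radiation when FOLFOX is given under physician discretion, or when neutropenia is found after the cycle has begun;
- which provision governs if any overlap remains.

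Aligning the paragraph with Table 11.1 alone would leave the grade 2 discrepancy with Table 11.3 in place. Which clinical rule to adopt is for the sponsor to decide; this review proposes none. The cost is a short protocol text amendment, with no change to the sample size, assessments or analysis.

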11.2 Chemotherapy

The patient will discontinue FOLFOX and be referred for treatment off protocol if the patient requires dose reduction beyond level -2 during cycles 1-5 of preoperative therapy or if FOLFOX is held due to toxicity for more than 30 days from the previous cycle.

The precise dose modification schema used and the symmetry of dose modification may be left to the discretion of the treatment physician.

Table 11.2 FOLFOX dose levels

Dose level*	5-FU infusion	5-FU bolus	Oxaliplatin
0	1200 mg/m ² /day x 2 days (2400 mg/m ² over 48 hours)	400 mg/m ²	85 mg/m ²
-1	960 mg/m ² /day x 2 days (1920 mg/m ² over 48 hours)	320 mg/m ²	65 mg/m ²
-2	800 mg/m ² /day x 2 days (1600 mg/m ² over 48 hours)	270 mg/m ²	50 mg/m ²
-3	680 mg/m ² /day x 2 days (1360 mg/m ² over 48 hours)	230 mg/m ²	40 mg/m ²

*Dose level 0 refers to the starting dose

Table 11.3 FOLFOX dose modifications based on adverse events

System/organ/class	Adverse event	Agent	Dosage change
Blood and lymphatic systemic disorders	Neutropenia grade ≥2 and/or Thrombocytopenia grade ≥ 2	5-FU Oxaliplatin	Hold up to 16 days until ANC ≥ 1200 K/mcL. If recovered in ≤ 16 days, then resume at next lower dose level. Hold up to 16 days until platelets ≥ 75,000 K/mcL. If recovered in ≤ 16 days, then resume at next lower dose level.
Gastrointestinal disorders	Nausea grade 2 Nausea grade 3	Oxaliplatin	Intensify antiemetic therapy and proceed with FOLFOX at current dose level. Maximal antiemetic therapy includes a 5-HT inhibitor in addition to Compazine, lorazepam, aprepitant, and dexamethasone If resolved to < grade 2 on day of treatment, may proceed with intensification of antiemetic therapy and current dose level of FOLFOX. If not resolved to < grade 2 on day of therapy, intensify antiemetic regimen

	Nausea grade 4	5-FU Oxaliplatin	and proceed with FOLFOX when resolved to < grade 2. May decrease oxaliplatin one dose level if not responsive to maximal antiemetic support.
Vomiting grade 2	If resolved to < grade 2 on day of treatment, may proceed with intensification of antiemetic therapy and current dose level of FOLFOX. If not resolved to < grade 2 on day of therapy, intensify antiemetic regimen and proceed with FOLFOX when resolved to < grade 2. Decrease oxaliplatin one dose level if not responsive to maximal antiemetic support.		
Vomiting grade 3	Intensify antiemetic therapy and proceed with FOLFOX at current dose level. Maximal antiemetic therapy includes a 5-HT inhibitor in addition to Compazine, lorazepam, aprepitant, and dexamethasone		
Vomiting grade 4	If resolved to < grade 2 on day of treatment, may proceed with intensification of antiemetic therapy and current dose level of FOLFOX. If not resolved to < grade 2 on day of therapy, intensify antiemetic regimen and proceed with FOLFOX when resolved to < grade 2. May decrease oxaliplatin one dose level if not responsive to maximal antiemetic support.		
Diarrhea grade 2	If resolved to < grade 2 on day of treatment, may proceed with intensification of antiemetic therapy and current dose level of FOLFOX. If not resolved to < grade 2 on day of therapy, intensify antiemetic regimen and proceed with FOLFOX when resolved to < grade 2. Decrease oxaliplatin one dose level if not		
Diarrhea grade 3			

	
Diarrhea grade 4
 
Oral mucositis, esophagitis, gastritis, pharyngeal mucositis, small intestinal mucositis, colitis, rectal and/or anal mucositis grade 3
 
Oral mucositis, esophagitis, gastritis, pharyngeal mucositis, small intestinal mucositis, colitis, rectal and/or anal mucositis grade 4
	
responsive to maximal antiemetic support.
 
If resolved to < grade 2, intensify antidiarrheal therapy and proceed with FOLFOX at current dose level. If not resolved to < grade 2, hold FOLFOX, intensify antidiarrheal therapy and proceed with FOLFOX when resolved to < grade 2.
 
If resolved to < grade 2, intensify antidiarrheal therapy and proceed with FOLFOX, decreasing 5FU and oxaliplatin one dose level. If not resolved to < grade 2, hold FOLFOX, intensify antidiarrheal therapy and proceed with FOLFOX decreasing 5FU one dose level when resolved to < grade 2.
 
If resolved to < grade 2, intensify antidiarrheal therapy and proceed with FOLFOX, decreasing 5FU and oxaliplatin one dose level. If not resolved to < grade 2, hold FOLFOX decreasing 5FU and oxaliplatin one dose level when resolved to < grade 2.
 
Hold FOLFOX until mucositis improves to < grade 2 then resume with one dose level reduction of 5-FU and the previous dose level of oxaliplatin
 
Hold FOLFOX until mucositis improves to < grade 2 then resume with two dose levels reduction of 5-FU and the previous dose level of oxaliplatin

--	---	--

Pulmonary disorders	Cough, dyspnea, hypoxia, pneumonitis or pulmonary infiltrates grade 3+	5-FU Oxaliplatin	Hold oxaliplatin until interstitial lung disease is ruled out. Continue 5-FU/leucovorin. Discontinue study if interstitial lung disease is confirmed.
Thrombotic microangiopathy	Hemolytic uremic syndrome grade 3+	5-FU Oxaliplatin	Discontinue oxaliplatin. Continue 5-FU/leucovorin.
Immune system disorders	Allergic reaction grade 1 Allergic reaction grade 2 Allergic reaction grade 3 or 4	Oxaliplatin Leucovorin	Decrease infusion rate by 50% until symptoms resolve, then resume at initial planned rate. Stop FOLFOX infusion. Administer H1 and/or H2 blockers and/or steroids according to local medical site policy. Restart infusion when symptoms resolve and pretreat before all subsequent doses. Stop infusion. Discontinue FOLFOX.
Skin and subcutaneous tissue disorders	Extravasation	Oxaliplatin	Extravasation of oxaliplatin has been associated with necrosis. If extravasation is suspected, stop the FOLFOX infusion and restart at another site.
Neurological	Neurotoxicity grade 2 persisting between treatment cycles Neurotoxicity grade 3 resolving to ≤grade 2 between treatment cycles Neurotoxicity grade 3 persisting between treatment cycles Neurotoxicity grade 4	Oxaliplatin	Continue FOLFOX with previous dose level of 5-FU and one dose level reduction of oxaliplatin for all subsequent cycles. Continue FOLFOX with previous dose level of 5-FU and one dose level reduction of oxaliplatin for all subsequent cycles. Discontinue oxaliplatin. Continue 5-FU/leucovorin. Discontinue oxaliplatin. Continue 5-FU/leucovorin.
Other non-hematologic	Grade 3 or 4	5-FU Oxaliplatin Leucovorin	Hold FOLFOX until toxicity ≤grade 1 then resume with one dose level reduction of both 5-FU and oxaliplatin.

The following describe actions in the Dosage Change column:

Omit = Treatment is not given for this cycle
Hold = Treatment can be made up as part of this cycle
Discontinue = Treatment is totally stopped

